9.5. Pregnancies

For any subjects in the Safety population who became pregnant during the study, every attempt will be made to follow these subjects to completion of pregnancy to document the outcome, including information regarding any complications with pregnancy and/or delivery. Listings of the total pregnancies; gravida and para; number of live births; number of still births; and number of spontaneous, elective, or therapeutic abortions will be presented ([Listing 12](#), [Listing 13](#), [Listing 14](#), [Listing 15](#), and [Listing 16](#)).

9.6. Clinical Laboratory Evaluations

Safety clinical laboratory measures will include measures of white blood cell (WBC), hemoglobin (Hgb), platelets, ALT, and creatinine. The clinical laboratory reference ranges will be provided in Section 12.4.1 and are found in Appendix B of the protocol. Clinical laboratories collected prior to confirmed HCV infection will be summarized separately from clinical laboratories collected after confirmed HCV infection. This separation will be defined as HCV infection status.

Laboratory abnormalities are those that meet toxicity grading. When the site-specific laboratory normal range is available, if there is a discrepancy between the laboratory value in Appendix B of the protocol and the site-specific laboratory normal range, the site-specific ranges will take precedence in determining Grade 1 adverse events. Otherwise, all laboratory tests will be graded per the toxicity table in Appendix B of the protocol as well as in [Table 124](#), [Table 125](#), [Table 126](#), and [Table 127](#). Unscheduled or repeated follow-up laboratory tests for medical or safety reasons will be listed, but excluded from tabular and graphical summaries.

The primary safety endpoint is occurrence of clinical safety laboratory adverse events assessed at baseline and 1 month following each vaccination. The number of subjects reporting at least one laboratory measurement at the visit, the proportion of subjects who experienced laboratory AEs, and the 95% Blaker confidence interval for the proportion of subjects who experienced laboratory AEs will be presented by treatment group. In addition, the difference in proportions between the AdCh3NSmut1/MVA-NSmut vaccine group and the placebo group and 95% Exact confidence intervals will be presented in [Table 85](#).

The proportion of subjects with laboratory results meeting toxicity grading criteria will be presented for each biochemistry and hematology parameter by HCV Infection status, visit, toxicity grade, and treatment group in [Table 86](#), [Table 87](#), [Table 90](#), and [Table 91](#), respectively. The proportion of subjects with laboratory results related to study product meeting toxicity grading criteria will be presented for each biochemistry parameter in [Table 88](#) and [Table 89](#) and each hematology parameter in [Table 92](#) and [Table 93](#) by HCV Infection status, severity, study day and treatment group. Descriptive statistics including mean, standard deviation, median, mean change from baseline and associated standard deviation by timepoint, for each laboratory parameter, will be summarized by HCV Infection status and treatment group in [Table 94](#), [Table 95](#), [Table 96](#), [Table 97](#), [Table 98](#), [Table 99](#), [Table 100](#), [Table 101](#), by treatment group. Laboratory values will be presented by visit and treatment group in [Figure 31](#), [Figure 32](#), [Figure 33](#), [Figure 34](#), [Figure 35](#), [Figure 36](#), [Figure 37](#), [Figure 38](#), [Figure 39](#), and [Figure 40](#). Shift tables by time point, based on the normal ranges provided by the clinical laboratory, are presented in [Table 102](#), [Table 103](#), [Table 104](#), and [Table 105](#).

The denominator for proportions is the number of subjects with each specific laboratory parameter at the visit. Additionally, graded results will be analyzed as a multinomial variable (Grade 0, Grade 1, Grade 2, Grade 3 and above) using ordinal logistic regression to make treatment group comparisons. The odds of a lab parameter being in a higher level severity among subjects receiving vaccine compared to placebo will be calculated ([Table 106](#), [Table 107](#), [Table 108](#), [Table 109](#)). The covariates that will be used are treatment group

and baseline laboratory severity. The proportional odds assumption will be tested to show whether or not the relationship between each pair of outcome groups is the same.

The model described above will be fit for each laboratory parameter and estimates of which factors influence severity at baseline and one month after each vaccination will be obtained using PROC LOGISTIC following the pseudocode in Section 6.1.1.

A listing of laboratory tests with toxicity Grade ≥ 2 will also be provided for biochemistry and hematology results. If a subject meets this criterion, the listing will provide data from all visits for the particular lab test that meet the criteria so that the time course for the particular lab parameter can be observed. See [Table 110](#) and [Table 111](#). A listing of all clinical laboratory values will be generated in [Listing 17](#) and [Listing 18](#).

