- Vital signs will be obtained, including oral temperature, pulse, and blood pressure.
- Medical history will be reviewed to assure continued eligibility.
- All concomitant medications will be reviewed for accuracy and completeness. Any new medications will be recorded and assessed for continuing eligibility.
- A targeted physical examination may be performed, as indicated, based on subject's recent clinical history since the screening visit.
- Behavioral risk will be assessed using an interviewer administered questionnaire.
- A urine or serum pregnancy test must be performed within 24 hours prior to vaccination for all female subjects of childbearing potential. Results must be negative and known prior to vaccination. If the screening visit is Day -1, a negative pregnancy test obtained at Day -1 may be used for eligibility at Day 0. If the pregnancy test is > 24 hours prior to vaccination, it must be repeated to determine eligibility.
- Approximately 8 mL of venous blood will be collected for HLA typing/genetic studies, as described in Section 7.6.1.

- Approximately 23 mL of venous blood will be collected prior to vaccination for hematology, coagulation and chemistry/metabolic biochemistry parameters, as described in Section 7.6.1. Clinical safety laboratory assessments will be performed by the local laboratory. The results from this blood draw will not be available or reviewed prior to vaccination, and will serve as a baseline safety assessment only.
- Approximately 160 mL of venous blood will be collected prior to vaccination for baseline immunology assessments.
- Plasma saved from the blood collected for immunology assessments at this visit will be used for anti-adenovirus Ab testing.
- Subjects will be enrolled in AdvantageEDC (IDES) and randomly assigned to a treatment arm.
- Subjects will receive a single dose of AdCh3NSmut1 vaccine or placebo per randomized assignment via intramuscular injection in the deltoid muscle of the preferred arm. Following vaccination the injection site will be covered with a sterile dressing and subjects will be observed in the clinic for at least 30 minutes. The vaccination site will be examined, and any AE/SAEs will be assessed prior to discharge from the clinic.

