3.2. Endpoints

The primary safety endpoints are as follows:

1. Occurrence of vaccine-related serious adverse events (SAEs) from the time of first vaccination through the entire study period.
2. Occurrence of severe local and/or systemic solicited reactogenicity signs and symptoms in the 8 days (Day 0-7) after each vaccination.
3. Occurrence of clinical safety laboratory adverse events (AEs) assessed at baseline and 1 month following each vaccination.

The occurrence of these safety parameters will be assessed by treatment group (vaccine and placebo).

The primary efficacy endpoint is:

1. Chronic HCV infection at 6 months defined by persistent viremia over a period of 6 months after detection of incident infection.

The secondary immunogenicity endpoint is:

1. The frequency of positive cell mediated immune response within 14 days after the last vaccination by treatment group (vaccine vs. placebo)

The exploratory efficacy endpoints are as follows:

1. An incident HCV infection will be defined as a new confirmed positive HCV RNA test after a previous negative HCV RNA test. The interval during which incident HCV infection occurs will be defined by the date of the last documented negative HCV RNA results, and the date of the first positive HCV RNA result.
2. Chronic HCV infection at 9 months defined by persistent viremia over a period of 9 months after detection of incident infection.
3. Quantitative viremia measures, including the incident peak and total HCV RNA levels detected, from the date of first HCV RNA detection and at study visits in the first 6 months of viremia will be compared, between vaccinated and placebo groups, using logarithmic IU/mL values.
4. The duration of incident infection will be defined as the interval between incident HCV infection and viral clearance. For subjects who do not clear HCV viremia, the duration will be measured as six months following incident infection. The interval during which incident HCV infection occurs will be defined by the date of the last documented HCV RNA negative results, and the date of the first positive HCV RNA result. The interval during which viral clearance occurs will be defined by the date of the last test with detectable HCV RNA and the first of two consecutive samples with undetectable HCV RNA.

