3.3.6. Baseline Value

The baseline value will be defined as the last value obtained prior to the first vaccination.

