- In the “If Not Related, Alternate Etiology” column, merge the 2 data fields for collecting alternate etiology, separate by a colon.
- Listing will include deaths, as they are SAEs, but we will also include a separate death listing below to highlight them

Tables with similar format:

Table 84: Listing of Deaths

Section 14.3.5 Displays of Laboratory Results

Table 85: Proportion of Subjects Reporting Laboratory Adverse Events Following the First Dose of Study Product by Treatment Group - Safety Population

Dose Number	Treatment Group	Number of Subjects with Laboratory AEs n	Number of Subjects N	Proportion of Subjects with Laboratory AEs	Proportion of Subjects with Laboratory AEs 95% CI	Difference in Proportion of Subjects with Laboratory AEs between Vaccine and Placebo	Difference in Proportion of Subjects with Laboratory AEs between Vaccine and Placebo 95% CI
Baseline	Vaccine	x	x	0.xx	0.xx, 0.xx	0.xx	0.xx, 0.xx
	Placebo	x	x	0.xx	0.xx, 0.xx	--	--
	All Subjects	x	x	0.xx	0.xx, 0.xx	--	--
Post Either Dose	Vaccine	x	x	0.xx	0.xx, 0.xx	0.xx	0.xx, 0.xx
	Placebo	x	x	0.xx	0.xx, 0.xx	--	--
	All Subjects	x	x	0.xx	0.xx, 0.xx	--	--
Post Dose 1	Vaccine	x	x	0.xx	0.xx, 0.xx	0.xx	0.xx, 0.xx
	Placebo	x	x	0.xx	0.xx, 0.xx	--	--
	All Subjects	x	x	0.xx	0.xx, 0.xx	--	--
Post Dose 2	Vaccine	x	x	0.xx	0.xx, 0.xx	0.xx	0.xx, 0.xx
	Placebo	x	x	0.xx	0.xx, 0.xx	--	--
	All Subjects	x	x	0.xx	0.xx, 0.xx	--	--

Notes: The denominator for proportions is based on the number of subjects enrolled in the safety population in the respective treatment group and dose number with non-missing laboratory data for the specified timepoint.

Table 86: Biochemistry Laboratory Results by Parameter, Maximum Severity, Visit, and Treatment Group – Safety Population-Uninfected HCV Status*

Visit	Laboratory Parameter	Toxicity Grade	Vaccine (N=X)		Placebo (N=X)		All Subjects (N=X)	
			n	%	n	%	n	%
Visit 1	Alanine Transferase (SGPT) (U/L)	Total Subjects with Data	x	100	x	x	x	x
		None	x	x	x	x	x	x
		Toxicity Grade 1	x	x	x	x	x	x
		Toxicity Grade 2	x	x	x	x	x	x
		Toxicity Grade 3	x	x	x	x	x	x
		Toxicity Grade 4	x	x	x	x	x	x
	Creatinine (mg/dL)	Total Subjects with Data	x	100	x	x	x	x
		None	x	x	x	x	x	x
		Toxicity Grade 1	x	x	x	x	x	x
		Toxicity Grade 2	x	x	x	x	x	x
		Toxicity Grade 3	x	x	x	x	x	x
		Toxicity Grade 4	x	x	x	x	x	x
Continue through Visit 26...								

Notes: * Uninfected HCV Status: all laboratory results collected prior to confirmed HCV infection are summarized

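### Table 85 counts graded laboratory values that were already present at the same grade before the first dose, and it cannot show worsening in a subject already graded at baseline

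*SAP*

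**What the plan says.** The endpoint in SAP 3.2 is "Occurrence of clinical safety laboratory adverse events (AEs) assessed at baseline and 1 month following each vaccination". SAP 9.6 repeats it as primary and gives one rule for what counts: "Laboratory abnormalities are those that meet toxicity grading". The result goes into Table 85, titled "Proportion of Subjects Reporting Laboratory Adverse Events Following the First Dose of Study Product by Treatment Group - Safety Population".

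The Table 85 shell has rows for Baseline, Post Either Dose, Post Dose 1 and Post Dose 2. Each row gives the number of subjects with laboratory AEs, the proportion, the difference between arms and a 95% CI; there is no p-value column. The denominator is safety subjects in the arm "with non-missing laboratory data for the specified timepoint", so subjects already graded at baseline stay in.

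Baseline is defined in SAP 3.3.6: "The baseline value will be defined as the last value obtained prior to the first vaccination". That is normally the Day 0 draw, of which Protocol 8.1.3 says: "The results from this blood draw will not be available or reviewed prior to vaccination, and will serve as a baseline safety assessment only".

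**The concern.** An adverse event under Protocol 9.2 arises in someone who has received a study intervention, and the Table 85 title refers to the time after the first dose. Yet its Baseline row applies the laboratory-AE label to values drawn before any dose. Nothing in SAP 9.6 or the shell removes those values from the later rows. Protocol 9.4 refers laboratory AEs to the laboratory's normal range and not to the subject's own earlier value.

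A subject with Grade 1 hemoglobin at Day 0 and again at Day 30 would therefore appear under Baseline, Post Dose 1 and Post Either Dose. Because Day 0 results are not seen before dosing, such subjects are vaccinated and enter the table. Randomization makes these carried-over values about equally common in both arms, so they carry no information on the vaccine but add variance to a primary safety summary. The yes/no count also hides worsening, which is a safety signal of interest. And since the rule is not explicit, two programmers could produce different versions of the table.

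**Working it through.** The plan gives no laboratory AE rate, no Day 0 prevalence and no precision target for Table 85, so there is no stated figure to reproduce.

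**1. Can a graded Day 0 value occur?** Appendix A sets the screening ranges and Appendix B the Grade 1 limits:

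| Parameter | Acceptable at screening | Grade 1 begins |
|---|---|---|
| ALT | up to 1.25 x ULN | above 1.25 x ULN |
| WBC (thou/mcl) | 3.0-10.8 | 2.9 or below; 11.9 or above |
| Platelets | 120K or more | 117K or below |
| Hemoglobin, women | 11.5 or more | 10.8 or below |
| Hemoglobin, men | 12.5 or more | 12.4 or below |
| Creatinine | not above normal | 1.2 x ULN |

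Site normal ranges override the eligibility ranges and the Grade 1 limits. A correctly enrolled subject is thus ungraded at screening. A graded Day 0 value must arise between screening and Day 0, at most 30 days (Protocol 8.1.2). It is possible, but should be uncommon.

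**2. Model.** All rates here are assumptions:
- *b* = proportion graded at Day 0, equal by arm: 1%, 2% or 10%.
- *q* = proportion of those still graded at the same level one month after dosing: 20% to 80%.
- *p* = new-onset rate among the rest: 3% placebo, 8% vaccine.
- *n* = 260 per arm with data (the target is 270).

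As written: P = *bq* + (1 − *b*)*p*. New grades only: P = (1 − *b*)*p*. In both cases the difference between arms is (1 − *b*)(*p*V − *p*P), because *bq* cancels.

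Half-width (Wald) = 1.96 × √{[PP(1 − PP) + PV(1 − PV)]/*n*}.

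Two simplifications: subjects graded at Day 0 either persist or resolve, so worsening is set to zero; and parameters are not separated.

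**3. One case in full, *b* = 10%, *q* = 80%.**
- As written: placebo 0.08 + 0.90 × 0.03 = 10.7%; vaccine 0.08 + 0.90 × 0.08 = 15.2%. Difference 4.5 points, ratio 15.2/10.7 = 1.42. Half-width 1.96 × √[(0.107 × 0.893 + 0.152 × 0.848)/260] = 5.8 points.
- New grades only: 2.7% and 7.2%. Difference 4.5 points, ratio 2.67. Half-width 1.96 × √[(0.027 × 0.973 + 0.072 × 0.928)/260] = 3.7 points.

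**4. Range.**

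| *b* | *q* | As written, placebo / vaccine | Difference, both rules | Half-width, as written | Half-width, new only | Ratio, as written (new only: 2.67) |
|---|---|---|---|---|---|---|
| 1% | 20% | 3.2% / 8.1% | 4.95 | 3.94 | 3.88 | 2.56 |
| 2% | 80% | 4.5% / 9.4% | 4.90 | 4.36 | 3.86 | 2.08 |
| 10% | 20% | 4.7% / 9.2% | 4.50 | 4.35 | 3.71 | 1.96 |
| 10% | 80% | 10.7% / 15.2% | 4.50 | 5.76 | 3.71 | 1.42 |

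With 270 per arm every half-width shrinks by √(260/270) = 0.98. The SAP plans exact intervals, so the Wald widths serve only to compare the two rules.

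**5. Worsening.** A subject at Grade 1 on Day 0 and Grade 3 at Visit 5 adds one to Baseline and one to Post Dose 1. A subject who stays at Grade 1 adds exactly the same.

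**The case against.** The case against has four parts.

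- **Baseline is used elsewhere.** Table 85 shows baseline proportions by arm. Tables 94-101 give change from baseline. Tables 102-105 count shifts from a normal baseline. Tables 106-109 compare arms one month after each dose by ordinal logistic regression with baseline severity as a covariate. A reader might infer that baseline is ignored, and that would be wrong. But all of Tables 94-109 work parameter by parameter, and none reports the proportion with any laboratory AE. The shift tables use normal ranges, not toxicity grades, and leave out subjects abnormal at baseline. The Baseline row is marginal and cannot separate persisting from new values within a subject.
- **The estimate is not biased.** A reader might infer that carry-over shrinks the reported excess. Under equal carry-over it does not: the absolute difference is the same under both rules. This part stands in full.
- **No power claim follows.** A reader might infer a large loss of power. SAP 9.6 plans no two-proportion test for this endpoint, whereas SAP 9.3.1 and 9.4 plan Fisher's exact test for the other two primary safety endpoints. Protocol 11.1 does promise a test of each primary safety endpoint, but the only laboratory test that the SAP specifies is the baseline-adjusted ordinal model. The screening limits also argue for a low Day 0 prevalence.
- **The rule is inferred.** The SAP nowhere states that an unchanged baseline abnormality counts after dosing. The reading comes from its silence together with the Baseline row and the denominator. That is the natural reading of the shell, but the sponsor may have meant otherwise, which is itself a reason to write the rule down.

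**Conclusion.** The point holds as one of precision and definition. As written, Table 85 mixes persisting with new abnormalities in a primary safety endpoint and cannot show worsening. Under equal carry-over the absolute difference is unaffected. What changes is the level of both proportions, the width of the interval and any relative measure.

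The size is uncertain because the documents give no Day 0 prevalence or persistence. At 1-2% graded at Day 0, which fits the screening limits better, the half-width is about 3.9-4.4 points instead of 3.9: little to modest. At 10% it is about 4.4-5.8 instead of 3.7. The documents do not support saying that the comparison is biased, that a material signal would be missed, or that baseline has been left out of the laboratory analyses.

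**What to change.** In SAP 9.6 and a footnote to Table 85, define a post-dose laboratory AE as a toxicity grade at Visit 5 or Visit 9 higher than the baseline grade for that parameter, with baseline as in SAP 3.3.6. That definition falls back on the screening value when Day 0 is missing. Keep the Baseline row and the any-grade Tables 86-91 as description. Name the ordinal models in Tables 106-109 as the baseline-adjusted comparison of the arms.

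The cost is one sentence, one footnote and one derived variable. The Day 0, Visit 5 and Visit 9 laboratory draws are already scheduled for all subjects, so no new data or visits are needed.

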9.2 Definitions

Adverse Event (AE)

An AE is any untoward medical occurrence in a clinical investigation subject who has received a study intervention and that does not necessarily have to have a causal relationship with the study product. An AE can, therefore, be any unfavorable and unintended sign (including an abnormal laboratory finding, for example), symptom, or disease temporally associated with the use of the study product, whether or not considered related to the study product.

Unexpected

An unexpected AE is an adverse reaction, the nature or severity of which is not consistent with the applicable product information (e.g., investigator's brochure [IB] for an unapproved investigational medicinal product). Unexpected refers to an experience that has not been previously observed. This includes events that are more serious than expected or occur more frequently than expected.

Expected

Any adverse experience, the nature, severity or frequency of which is consistent with the current IB; or with the risk information described in the investigational plan or protocol or consent form.

Serious Adverse Event (SAE)

An adverse event or suspected adverse reaction is considered "serious" if, in the view of either the investigator or sponsor, it results in any of the following outcomes:

- Death,
- A life-threatening adverse event*,
- Inpatient hospitalization or prolongation of existing hospitalization,
- A persistent or significant incapacity or substantial disruption of the ability to conduct normal life functions, or
- A congenital anomaly/birth defect.
- Important medical events that may not result in death, be life-threatening, or require hospitalizations may be considered serious when, based upon appropriate medical judgment, they may jeopardize the subject and may require medical or surgical intervention to prevent one of the outcomes listed in this definition. Examples of such medical events include allergic bronchospasm requiring intensive treatment in an emergency room or at home, blood dyscrasias or convulsions that do not result in subject hospitalization, or the development of drug dependency or drug abuse.
- * Life-threatening adverse event. An adverse event is considered "life-threatening" if, in the view of either the investigator or sponsor, its occurrence places the subject or subject at immediate risk of death. It does not include an adverse event, had it occurred in a more severe form, might have caused death.

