9.4 Investigator's Assessment of Adverse Events

The determination of seriousness, severity, and causality will be made by an onsite investigator who is qualified (licensed in the state) to diagnose adverse event information, provide a medical evaluation of adverse events, and classify adverse events based upon medical judgment. This includes but is not limited to physicians, physician assistants, and nurse practitioners. Laboratory abnormalities will be reported as AEs based on the normal range of values for the laboratory. The grading of the laboratory AEs will be based on the DMID toxicity table (Appendix B).

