4.5. Efficacy, Immunogenicity, and Safety Variables

See Section 3.3 for efficacy and immunogenicity variable definitions.

The safety variables to be assessed are reactogenicity events, unsolicited adverse events (AEs), serious adverse events (SAEs), and protocol specified clinical safety laboratory, physical exam, and vital sign parameters.

Subjects were to record temperature and the presence and intensity of post-vaccination reactogenicity events daily on an 8-day subject memory aid. Local solicited reactogenicity events include: pain, tenderness, erythema, induration and warmth at the injection site. Systemic solicited reactogenicity events include: fever, chills, arthralgia/joint pain, malaise/fatigue, myalgia/body aches, headache, nausea, vomiting, abdominal pain. Erythema and induration at the vaccination site will be measured in millimeters and functional grade. Any symptoms still present at Day 7 will continue to be followed until symptom resolution.

Solicited reactogenicity symptoms will be graded using the scale in section 9.4.4 of the protocol.

Unsolicited adverse event severity will be graded according to parameters shown in Appendix B of the protocol or if graded differently this will be noted in the tables using the definitions in section 9.4.2 of the protocol.

Clinical laboratory evaluations for safety will be performed by local (clinical) laboratories. Venous blood samples will be collected from each subject prior to each vaccination and according to the Study Schedule in Appendix C of the protocol. Clinical safety lab parameters to be followed include WBC, HgB, platelets, ALT, and creatinine. Urine will be collected to evaluate glucose and protein, which will be performed at screening only. Toxicity grades for each clinical laboratory parameter can be found in Appendix B of the protocol.

Multiple observations within a specific visit period are accepted. In the case of multiple observations within a specific window, the assessment value that is closest to the scheduled visit will be used in the analyses for the post-baseline records. For screening and baseline visits, the last assessment value prior to first vaccination will be used as the baseline measurement. All the recorded data will be listed. If observations have the same distance to the scheduled assessment, the latest one will be used.

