9.3. Adverse Events

When calculating the incidence of solicited and unsolicited adverse events (i.e., on a per subject basis), each subject will only be counted once and any repetitions of adverse events within a subject will be ignored; the denominator will be the number of subjects who received study vaccination with non-missing data for the event summarized within actual treatment group. All adverse events reported will be included in the summaries and analyses. All analyses in Section 9.3 will be performed in the safety analysis population using vaccine group if a subject received one or more doses of vaccine and placebo group otherwise.

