- For all adverse events (solicited, unsolicited, or laboratory events) occurring in 5% of subjects in any treatment group, the frequency of each event will be presented by MedDRA® system organ class, preferred term, and treatment group in [Table 74](#).
- For all adverse events (solicited, unsolicited, or laboratory events) occurring in 5% of subjects in any treatment group, the number and percentage of subjects reporting each event presented by SOC, PT, and treatment group in [Table 75](#).

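### SAP 9.6 keeps safety-prompted off-schedule laboratory tests out of every summary, so after about Day 90 a non-serious abnormality seen only on such a test has no count by arm

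*SAP*

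**What the plan says.** SAP 9.6 sets the rule: "Unscheduled or repeated follow-up laboratory tests for medical or safety reasons will be listed, but excluded from tabular and graphical summaries". The same section lays out the toxicity-grade tables "by HCV Infection status, visit, toxicity grade, and treatment group". SAP 4.5 settles which value represents a visit when there are several: "In the case of multiple observations within a specific window, the assessment value that is closest to the scheduled visit will be used".

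The excluded values are not lost. Listings 17-18 hold all laboratory values. For subjects with a Grade 2 or higher result, Tables 110-111 add a time course: "the listing will provide data from all visits for the particular lab test that meet the criteria". All four displays show the treatment arm.

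There is also an adverse-event route. Protocol 9.2 defines an AE broadly ("including an abnormal laboratory finding, for example"), and Protocol 9.4 adds: "Laboratory abnormalities will be reported as AEs based on the normal range of values for the laboratory". SAP 9.3 then says: "All adverse events reported will be included in the summaries and analyses". This route is limited in time. Protocol 9.3.1 and SAP 9.3.2 stop collecting non-serious AEs at about Day 90, and after that only SAEs continue into the AE tables.

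**The concern.** A test ordered for a medical or safety reason is one that somebody had cause to order, and it is this kind of test that the summaries leave out. Protocol 3.1.1 names safety signal detection as the main purpose of the safety evaluations. A listing lets a reader find individual cases, but it gives no denominator, percentage or interval. Anyone wanting to compare arms on these values would have to count by hand. At stake is a descriptive safety comparison late in follow-up; no endpoint or test is involved.

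**Working it through.** The documents give no figure to reproduce. The check is whether any planned display counts, by arm, an abnormality found only on an off-schedule safety draw.

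**1. Laboratory displays in SAP 9.6 and Appendix 1**

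| Display | Structure | Counts such a value by arm? |
|---|---|---|
| Table 85 | Any laboratory AE, yes or no, no grade; serves the endpoint at baseline and 1 month after each dose | No |
| Tables 86-93 | Grade by visit. The titles mention maximum severity, but the shells run Visit 1 to Visit 26, or the first HCV RNA positive visit and H01 to H09 | No |
| Tables 94-101, Figures 31-40 | Summary statistics and plots by visit | No |
| Tables 102-105 | Shifts from baseline by visit | No |
| Tables 106-109 | Ordinal models at 1 month after each dose | No |
| Tables 110-111 | Listing of Grade 2 or higher results, with arm | Shown, not counted |
| Listings 17-18 | All values, with arm | Shown, not counted |

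No row or column anywhere gives a subject's worst grade over the post-dose period.

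**2. Does the SAP 4.5 window rule bring these values back?** At most in part. It applies only to draws inside a scheduled window, and it picks the value nearest the target day. A higher value elsewhere in the window is passed over.

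**3. Dose 1 to about Day 90.** Protocol 9.2 and 9.4 make the abnormality a reportable AE, graded by the protocol's toxicity table. SAP 9.3 puts all reported AEs into the summaries. Tables 62, 64 and 66 give unsolicited AEs by preferred term, highest severity and arm. On this plain reading the abnormality is counted.

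**4. After about Day 90.** A serious event is still tabulated by arm (Tables 76, 78, 80 and 82). A non-serious abnormality is no longer collected as an AE. Protocol 9.3.1 also collects new-onset chronic illnesses to the last visit, but SAP section 9 names no table for them. Only the listings in step 1 remain.

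**5. How much scheduled testing covers the late period?** In Protocol Appendix C, HCV-uninfected subjects have haematology and biochemistry after Visit 9 at Visit 10 (Day 120), Visit 16 (Day 300) and Visit 26 (Day 600). The intervals between target days are 300 − 120 = 180 days and 600 − 300 = 300 days. Protocol 8.5.1 adds a draw at early termination. In Appendix D, HCV-infected subjects have both panels at every visit from H01 to H09, about every 30 days, so little can fall between their visits.

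**The case against.** The case for leaving the plan alone has real weight.

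- **Scheduled-only displays are sound.** Tests done on indication come at irregular times and may be more frequent in one arm, so keeping them out of by-visit means, plots, shifts and models is defensible. This stands, and the fix leaves those displays alone.
- **The late gap comes partly from protocol design.** The protocol chose to stop non-serious AE collection at about Day 90, and later abnormalities are less likely to be vaccine-related. This stands and limits the weight of the point.
- **There are safeguards.** Under Protocol 9.6, one Grade 3 laboratory value judged related to vaccination triggers a safety review, and SAEs are tabulated throughout. This stands.
- **Unscheduled visits need not involve blood.** Protocol 8.4 allows them at any time but prescribes no laboratory draw. Repeats that follow an AE recorded before Day 90 concern an event already counted. This is why the number of affected values may be nil.

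Stronger readings are tempting, and the documents do not support them.

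- A reader might infer that abnormalities before Day 90 also go uncounted, because SAP 9.3.2 names laboratory events separately in the filtered Tables 74-75 ("For all adverse events (solicited, unsolicited, or laboratory events) occurring in 5% of subjects in any treatment group"). Naming them there does not remove them from the other AE tables, and SAP 9.3 says all reported AEs are included.
- A reader might take the calendar time outside the late visit windows as the share of laboratory data lost. Days are not values or subjects. Early-termination draws fill some of that time, and the exclusion reaches only tests done for medical or safety reasons. A make-up draw after a missed visit is not one of those.
- A reader might see a conflict with Protocol 11.4.2, which plans laboratory summaries by arm and grade. That section says nothing about unscheduled tests, so the SAP rule does not contradict it.

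**Conclusion.** The point holds in a narrow form. No planned table gives a worst post-dose laboratory grade by arm. After about Day 90, a non-serious abnormality seen only on an unscheduled or repeat test done for medical or safety reasons is listed with its arm but not counted. The exposure lies mainly with HCV-uninfected subjects, who have three scheduled safety-laboratory visits after Visit 9.

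The size cannot be estimated, because the documents give no rate of such draws; it may be nil. The 1-month primary laboratory endpoint in Table 85 does not change, and neither does any test or model. The conclusion assumes the plain reading of SAP 9.3, under which laboratory AEs up to about Day 90 enter the AE tables. This is a cheap improvement to descriptive safety reporting, and the trial's conclusions do not depend on it.

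**What to change.** Keep Table 85 and all by-visit tables, figures, shift tables and ordinal models on scheduled samples. Add to SAP 9.6 a small set of descriptive companion tables for biochemistry and haematology, split by HCV infection status as SAP 9.6 defines it, so that ALT rises from acute HCV are not mixed in. By arm, each table would give:

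- the number and percentage of subjects by highest post-dose grade for each parameter, from any sample, exempt from the SAP 4.5 nearest-value rule;
- the same count from scheduled samples only, alongside;
- the number of subjects with any unscheduled draw.

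Use 95% Blaker intervals, as elsewhere in the safety analysis, and no test. A sentence in SAP 9.3.2 confirming whether laboratory AEs enter Tables 58-72 would help but is optional.

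The cost is a few extra tables: two panels by two infection statuses makes four in the layout of Tables 86, 87, 90 and 91. They use data already needed for Listings 17-18, with no new collection and no endpoint change. The downside is that testing may differ between arms. The side-by-side counts would reveal this but not remove it, so the tables should be read descriptively.
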